10.4 Secondary Efficacy Analyses

The secondary efficacy endpoints are:

- The percentage of subjects with on-treatment virologic failure;
- The percentage of subjects with Relapse₁₂.

The number and percentage of subjects with on-treatment virologic failure and Relapse₁₂ in the ITT population will be summarized along with two-sided 95% Wilson score CIs.

10.5 Sensitivity Analyses for SVR

As sensitivity analyses, the number and percentage of subjects in the mITT-VF population achieving SVR₁₂ will be summarized along with two-sided 95% CIs using the normal approximation to the binomial distribution and the Wilson's score method.

A different CI from that used for the primary analysis will be calculated for the primary endpoint of SVR₁₂ based on the ITT population as a sensitivity analysis. If the number of SVR₁₂ non-responders is ≥ 5 , then the two-sided 95% CI using Wilson's score method will be calculated. If the number of SVR₁₂ non-responders is < 5 , the two-sided 95% CI using the normal approximation to the binomial distribution will be calculated.

Listings of subjects excluded from the mITT-VF population will be provided, as applicable.

10.6 Efficacy Subgroup Analysis

The percentage of subjects with SVR₁₂ in the ITT population will be presented. Two-sided 95% Wilson score CIs will also be presented for the following subgroups if there are at least 10 subjects in the subgroup:

- HCV genotype (1, 2, 3, 4, 5, 6, mixed, or unknown) (based on final HCV genotype and subtype determination specified in Section 10.8);
- DAA-containing regimen received in the AbbVie HCV parent study (ABT-493/ABT-530, 3D or 2D);
- Previous treatment experience prior to enrolling in the AbbVie HCV parent study:
 - Treatment naïve/DAA-naïve
 - Treatment experienced, PI-experienced only
 - Treatment experienced, NS5Ai-experienced only
 - Treatment experienced, PI- and NS5Ai-experienced
 - Treatment experienced, NS5Bi-experienced only
 - Treatment experienced, NS5Bi- and PI-experienced

- Treatment experienced, NS5Bi- and NS5Ai-experienced
- Treatment experienced, NS5Bi-, PI- and NS5Ai-experienced
- Baseline fibrosis stage (equivalent to Metavir F0 – F1, F2, F3, or F4);
- Baseline HCV RNA level ($< 1,000,000$, $\geq 1,000,000$ to $< 2,000,000$, or $\geq 2,000,000$ IU/mL).

10.7 Additional Efficacy Analyses

The following additional efficacy endpoints will be summarized for the ITT population:

- The percentage of subjects with HCV RNA $<$ LLOQ at each post-baseline visit in the Treatment Period (using data as observed);
- The percentage of subjects with SVR₄;
- The percentage of subjects with SVR₂₄;
- The percentage of subjects who relapse after achieving SVR₁₂ (**Relapse₂₄**).
- The percentage of subjects with virologic failure through Post-Treatment Week 24 (i.e., the SVR₂₄ non-responders due to **on-treatment virologic failure** or **Relapse_{overall}**).

For each of the above endpoints, a two-sided 95% CI using Wilson's score method will be calculated along with the number and percentage of subjects. Imputations for missing data will be performed as described in Section 6.3 for all the additional endpoints listed above except the first one.

For the ITT population, a summary of the subjects who completed treatment and relapsed (defined as **Relapse_{overall}**) will be prepared displaying the number of subjects relapsing at any timepoint and by the SVR visit window where the first relapse occurred (within the SVR₄, SVR₁₂, or SVR₂₄ window or after the SVR₂₄ window); subject numbers will be listed. A similar summary will be prepared for subjects who prematurely discontinued treatment and relapsed after having HCV RNA $<$ LLOQ at their Final Treatment Visit.

The number and percentage of subjects who do not achieve SVR₂₄ will be summarized by reason for non-response (as defined in Section 10.1) for the ITT population. A listing of subject numbers and reason for non-response will be prepared.

The concordance between SVR₁₂ and SVR₂₄ will be assessed for the overall population (across genotype and treatment arm) by the agreement between SVR₁₂ and SVR₂₄ and the positive predictive value (PPV) and negative predictive value (NPV) of SVR₁₂ on SVR₂₄. The agreement between SVR₁₂ and SVR₂₄ is a percentage defined as the number of subjects achieving both SVR₁₂ and SVR₂₄ and the number of subjects where both SVR₁₂ and SVR₂₄ are not achieved. The PPV of SVR₁₂ on SVR₂₄ is the proportion of subjects who achieve SVR₂₄ out of all subjects who achieved SVR₁₂. The NPV of SVR₁₂ on SVR₂₄ is the proportion of subjects who do not achieve SVR₂₄ out of all subjects who did not achieve SVR₁₂. Similarly, the concordance between SVR₄ and SVR₁₂ will be summarized for the overall population.

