6.3 Missing Data Imputation

Missing Data Imputation for SVR

HCV RNA values will be selected for analysis based on the analysis windows defined in Section 6.2.

For analyses of SVR, subjects' missing visit values will have backward imputation applied, if possible. For backward imputation, if the nearest HCV RNA value after the SVR window is unquantifiable or undetectable, then it will be used to impute the HCV RNA value in the SVR window. If a subject is missing an HCV RNA value within the appropriate SVR window after performing backward imputation, then this value will be imputed with an HCV RNA value from a local laboratory if present; otherwise, the HCV RNA value will be missing. Subjects with missing HCV RNA data in the analysis window, after imputations, will be imputed as a failure.

Regardless of the imputation method described above, if a subject starts another treatment for HCV, then all HCV RNA values for this subject measured on or after the start date of the new HCV treatment will be excluded from analyses. The subject will be considered a failure for summaries of viral response at all time points after the start of the new HCV treatment.

Missing Data Imputation for Virologic Failure

If HCV RNA values from the central laboratory are missing but a local laboratory value is present in the appropriate time period, then the local laboratory value will be used to assess post-treatment relapse and on-treatment virologic failure.

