10.0 Efficacy Analysis

10.1 General Considerations

General Considerations

All efficacy analyses will be performed on the ITT population by treatment arm and overall, unless otherwise specified. To support the primary analysis, sensitivity analyses will also be conducted using the mITT-VF population.

Missing data will be imputed as described in Section 6.3 for analyses of the HCV RNA endpoints of SVR and virologic failure.

Plasma HCV RNA levels will be determined for each sample collected by the central laboratory using the Roche COBAS® AmpliPrep/COBAS® TaqMan® HCV Quantitative Test, v2.0. The lower limit of detection (LLOD) and lower limit of quantification (LLOQ) for this assay (regardless of genotype) are both 15 IU/mL.

HCV RNA results that are detectable but not quantifiable are reported as "< 15 IU/ML HCV RNA DETECTED" and those that are undetectable are reported as "HCV RNA NOT DETECTED" in the database.

The notation "HCV RNA < LLOQ" is used to represent all HCV RNA values < 15 IU/mL, including values reported as "HCV RNA NOT DETECTED" or "< 15 IU/ML HCV RNA DETECTED." HCV RNA \geq LLOQ are all quantifiable values of 15 IU/mL or greater.

Definitions for Efficacy Endpoints

A confirmed quantifiable value during treatment is defined as any two consecutive HCV RNA measurements \geq LLOQ (or 100 IU/mL for **Breakthrough**), either both during treatment or at the final treatment measurement and the next consecutive post-treatment measurement. A confirmed quantifiable post-treatment value is defined as any two consecutive post-treatment HCV RNA measurements \geq LLOQ.

Breakthrough = confirmed HCV RNA \geq 100 IU/mL after HCV RNA < LLOQ during the Treatment Period; or confirmed increase from nadir in HCV RNA (two consecutive HCV RNA measurements > 1 log₁₀ IU/mL above nadir) at any time point during the Treatment Period. A single breakthrough value (\geq 100 IU/mL or > 1 log₁₀ above nadir) followed by lost to follow-up also will be considered a breakthrough (i.e., will not require confirmation).

EOT failure = HCV RNA \geq LLOQ at end of treatment with at least 6 weeks of treatment, where the HCV RNA value must be collected on or after Study Drug Day 36 and study drug duration \geq 36 days.

On-treatment virologic failure = Breakthrough or EOT failure; if a subject meets both definitions of Breakthrough and EOT failure, he or she will be categorized as Breakthrough only.

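### SAP 10.7 computes SVR concordance and PPV on imputed SVR status, so a missed later visit counts as discordance and a back-filled earlier visit as agreement

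*SAP*

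**What the plan says.** The last paragraph of SAP 10.7 defines the concordance measures for all subjects, across genotype and arm. For the positive direction, "The PPV of SVR₁₂ on SVR₂₄ is the proportion of subjects who achieve SVR₂₄ out of all subjects who achieved SVR₁₂". For the negative direction, "The NPV of SVR₁₂ on SVR₂₄ is the proportion of subjects who do not achieve SVR₂₄ out of all subjects who did not achieve SVR₁₂". Agreement counts subjects who are successes on both endpoints or failures on both. The earlier pair follows the same method: "Similarly, the concordance between SVR₄ and SVR₁₂ will be summarized for the overall population".

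The paragraph does not mention missing data, but the rules around it do. SAP 10.1 says "Missing data will be imputed as described in Section 6.3 for analyses of the HCV RNA endpoints of SVR and virologic failure". Earlier in SAP 10.7, after the list of additional endpoints that includes SVR4 and SVR24, the plan adds "Imputations for missing data will be performed as described in Section 6.3 for all the additional endpoints listed above except the first one"; the exempted item is on-treatment response.

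SAP 6.3 sets the order of imputation. First, "if the nearest HCV RNA value after the SVR window is unquantifiable or undetectable, then it will be used to impute" the value in the SVR window. Next, a local laboratory value is used if there is one. Last, "Subjects with missing HCV RNA data in the analysis window, after imputations, will be imputed as a failure".

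SAP 10.1 treats late relapse differently. Relapse24 is confined to SVR12 responders who have HCV RNA data in the SVR24 window, and missing SVR24 follow-up is a separate reason for SVR24 non-response.

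**The concern.** Missing-as-failure is a familiar, cautious rule for a response rate. A predictive value asks something else: among subjects with the earlier response, how often does the later measurement confirm it? If an absent later measurement is coded as failure, the PPV mixes loss of response with loss of follow-up. If an absent earlier measurement is filled from the later one, the pair compares a sample with itself.

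The study plans about 50 subjects, and SAP 4.3 expects fewer than 5 SVR12 non-responders. With so few true events, one or two missed Post-Treatment Week 24 visits can move the PPV as much as one or two genuine late relapses would, and the PPV alone does not show which occurred.

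**Working it through.** **The plan's own figures.** The documents state no expected agreement, PPV, NPV or missed-visit rate. The nearest stated figures are the Wilson intervals in SAP Table 3, and all 15 cells reproduce to 0.1 point. For example, with 0 failures in 50 the lower limit is 50/(50 + 1.96²) = 50/53.84 = 92.9%, as printed. The argument below uses no interval, because the SAP plans none for PPV or NPV.

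**Inputs.** From SAP Table 5, in days after the last dose: SVR4 window 3 to 56, SVR12 window 57 to 126, SVR24 window 127 to 210, with the last value in each window used. From SAP 4.2: one scheduled visit each at Post-Treatment Weeks 4, 12 and 24. From SAP 6.3: the imputation order above. From SAP 10.1: each SVR endpoint also requires no confirmed quantifiable post-treatment value before or during its window.

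**Rules applied to the missing-data patterns, scheduled visits only.**

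| SVR12 window | SVR24 window | SVR12 / SVR24 as planned | Effect |
|---|---|---|---|
| below LLOQ | empty, nothing later, no local value | yes / no | discordant; lowers PPV and agreement |
| empty | one sample, below LLOQ | yes (back-filled) / yes | agrees; one sample decides both |
| empty | empty, nothing later, no local value | no / no | agrees; adds 1 to NPV numerator and denominator |

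Running every pattern of below LLOQ, quantifiable and missing on the planned schedule, back-filled SVR12 agreed with SVR24 in 3 of 3 patterns, and back-filled SVR4 agreed with SVR12 in 4 of 4. SVR4 achieved with SVR12 missing and not back-filled behaves like the first row.

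**PPV.** Let R be the SVR12 responders and k those among them with no value for the SVR24 window, and assume no late relapse. Planned PPV = (R − k)/R. Observed-pairs PPV = (R − k)/(R − k) = 100%.

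- Main illustration (assumed): N = 50, R = 47, k = 3. Planned PPV = 44/47 = 93.6%; observed pairs 44/44 = 100%; Relapse24 = 0/44.
- Agreement in the same case, if the other 3 subjects fail both endpoints and the denominator is all 50 (SAP 10.7 does not state one): (44 + 3)/50 = 94.0%.
- Range (assumed): N = 50, 2 virologic failures by Week 12, so R = 48.

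| k | Planned PPV | Planned agreement | Observed-pairs PPV |
|---|---|---|---|
| 1 | 47/48 = 97.9% | 98% | 47/47 = 100% |
| 2 | 46/48 = 95.8% | 96% | 46/46 = 100% |
| 3 | 45/48 = 93.8% | 94% | 45/45 = 100% |
| 5 | 43/48 = 89.6% | 90% | 43/43 = 100% |

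**Back-fill.** With R = 48 and one true late relapse, planned PPV is 47/48 = 97.9%. If 1, 2 or 3 of the 47 concordant responders owed SVR12 to back-fill, observed-pairs PPV is 46/47 = 97.9%, 45/46 = 97.8% or 44/45 = 97.8%. This effect is real but small beside missing-as-failure.

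**NPV.** With 2 relapses by Week 12 and 1, 2 or 3 early dropouts (assumed), NPV is 3/3, 4/4 or 5/5. The percentage stays at 100%, while 1/3 = 33%, 2/4 = 50% or 3/5 = 60% of the count is missing data alone.

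**The case against.** The strongest reply is that this is a minor descriptive analysis whose artefact the plan already discloses. Concordance is neither a study objective nor a protocol endpoint, and SAP 10.2 states that there is no hypothesis testing. SAP 10.7 also tabulates SVR24 non-response by reason and lists the subjects, so treatment completers with missing follow-up can be told apart from relapsers. The SVR24 window spans 84 days (127 to 210), and a later or local value can rescue a missed visit. Missing-as-failure is cautious for PPV and matches the rule for every SVR endpoint. An observed-only PPV may flatter durability if those who drop out are likelier to relapse.

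All of that stands as mitigation. It limits the importance of the point and argues for keeping an imputed row. But the reason tables let a reader work around the reported PPV and agreement without correcting either, and caution in one direction does not describe a rule set that also creates agreement through back-fill and double absence.

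Several stronger readings are tempting and not supported:

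- *Dropouts raise the NPV.* A confirmed relapse by Week 12 is already an SVR24 failure by definition, and a missing SVR12 followed by a value below LLOQ normally becomes a success and leaves the denominator. NPV is therefore normally 100% anyway; exceptions need something like a single unconfirmed quantifiable value that later clears.
- *Back-fill always guarantees agreement.* It does so when the later window holds one sample, as scheduled. Back-fill takes the nearest later value and SVR24 takes the last, so a missed Week 12, below LLOQ on day 140 and quantifiable on day 200 gives SVR12 yes, SVR24 no.
- *Relapse24 of 0/44 contradicts a PPV of 44/47.* The denominators differ, and the planned tables reconcile them.
- *The analysis measures only attendance.* With complete data it measures SVR concordance.

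**Conclusion.** The point holds for agreement and PPV, in both the SVR12–SVR24 and SVR4–SVR12 comparisons. Each earlier responder with no central, later or local value for the later window lowers both measures with no virologic event. In the illustrations, 1 to 5 such subjects among 48 responders take the PPV from 100% to between 97.9% and 89.6%. Back-fill adds pairs that agree by construction under the planned schedule, with a small effect on PPV. Subjects missing both windows add agreement and enlarge the NPV count, usually leaving its percentage unchanged.

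The conclusion rests on reading SAP 6.3 into the concordance paragraph. That paragraph does not restate imputation, but SAP 10.1 applies it to SVR analyses and nothing in 10.7 switches it off for concordance. The missed-visit counts are assumptions. The primary SVR12 analysis, the SVR24 rate and the relapse analyses are unaffected. The change is still worth making, because the SAP already requires observed SVR24 data for Relapse24 and the same discipline is easily extended.

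**What to change.** In SAP 10.7:

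1. Compute agreement, PPV and NPV among subjects with an observed HCV RNA value in both windows, without backward imputation or missing-as-failure, and state the denominator for agreement.
2. Classify subjects with documented virologic failure before the later window as failures at the later time point even if no later sample exists. SAP 6.3 discards values after new HCV treatment starts, so a purely observed rule could drop true failures. Their agreement is then automatic, so report how many there are.
3. Report the number of subjects excluded for missing data.
4. Apply the same rules to SVR4–SVR12.
5. Optionally keep the imputed version as a labelled secondary row, since observed-only results could overstate durability if loss to follow-up is informative.

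The cost is a few lines of SAP text, one population flag and slightly smaller denominators. No data collection changes.

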10.8 Resistance Analyses

10.8.1 HCV Drug-Resistance Analyses

For all subjects, full length NS3/4A and NS5A will be sequenced from baseline samples by next generation sequencing (NGS). For all subjects who experience virologic failure (on-treatment virologic failure or Relapse_{overall} as defined in Section 10.1), full length NS3/4A, NS5A and NS5B genes from the first sample after virologic failure with HCV RNA \geq 1000 IU/mL will be sequenced by NGS. For all other subjects who do not achieve SVR₁₂ or SVR₂₄ (for non-virologic failure reasons as defined in Section 10.1) but have a post-treatment time point with HCV RNA \geq 1000 IU/mL, full length NS3/4A, NS5A and NS5B genes from the first post-treatment sample with HCV RNA \geq 1000 IU/mL will also be sequenced by NGS.

For all subjects who do not achieve SVR₁₂ or SVR₂₄, a listing by subject that includes HCV genotype/subtype, reason for SVR₁₂ or SVR₂₄ non-response, baseline resistance data availability, and key baseline characteristics will be produced by treatment arm.

For each DAA target, signature amino acid positions and the key subset of amino acid positions for the respective inhibitor class are shown in Table 10. Appropriate subtype-specific prototypic reference sequences will be used for comparison with sequences from samples.

Table 10. Signature Amino Acid Positions and the Key Subsets of Amino Acid Positions

Target	Signature Amino Acid Positions	Key Subset of Amino Acid Positions
GT1 NS3	36, 43 (GT1a only), 54, 55, 56, 80, 107, 122, 132 (GT1a only), 155, 156, 158, 168, 170, 175 (GT1b only)	155, 156, 168 (all GTs)
GT2, 3, 4, 5, 6 NS3	36, 43, 54, 55, 56, 80, 155, 156, 166 (GT3 only), 168	
GT1 NS5A	24, 28, 29, 30, 31, 32, 54 (GT1b only), 58, 62, 92, 93	24, 28, 30, 31, 58, 92, 93 (all GTs)
GT2, 3, 4, 5, 6 NS5A	24, 28, 29, 30, 31, 32, 58, 92, 93	
GT1, 2, 3, 4, 5, 6 NS5B	96, 142, 159, 237, 282, 289, 320, 321	282

Included time points for analyses of samples from subjects who do not achieve SVR₁₂ are 1) the sample closest in time after failure/discontinuation with an HCV RNA level of ≥ 1000 IU/mL, and 2) 24 weeks post-DAA treatment, provided that resistance-associated substitutions were detected at the time of failure/discontinuation.

The following definitions will be used in the resistance analyses:

- Baseline polymorphism: a polymorphism by NGS in a baseline sample ($\geq 2\%$ or $\geq 15\%$ prevalence within a subject's viral population depending on polymorphism frequency threshold utilized) that was not present in the appropriate prototypic reference amino acid sequence for a given DAA target (NS3, NS5A, or NS5B).
- Post-baseline substitution: an amino acid substitution in a post-baseline time point sample that was not detected at baseline ($< 2\%$) in the subject and is detectable in $\geq 2\%$ of the sequences from the post-baseline sample.

- Enriched variant: a variant present in both the baseline and a post-baseline sample whose prevalence in the post-baseline sample is at least 20 percentage points greater than the prevalence in the baseline sample [(post-baseline % – baseline %) \geq 20]
- Treatment-emergent substitution: A post-baseline substitution or an enriched variant.
- Substitution at signature amino acid position: a substitution in a post-baseline sample observed at \geq 2% prevalence within a subject's viral population that was not present in the appropriate prototypic reference amino acid sequence for a given DAA target (NS3/4A, NS5A, or NS5B).

Analysis 1

The following analyses will be performed for all subjects, separated by arm, HCV genotype/subtype, and previous treatment experience prior to enrolling in the AbbVie HCV parent study (including total):

- A listing of baseline polymorphisms (2% detection threshold) at signature amino acid positions for each DAA target (NS3, NS5A, and NS5B) in the ITT population. HCV genotype/subtype and treatment outcome (SVR₁₂ or reason for SVR₁₂ non-response) will also be displayed for each subject.
- The number and percentage of subjects with baseline polymorphisms at signature amino acid positions at detection thresholds of 2% and 15% for subjects in the ITT population. This analysis includes prevalence of each baseline polymorphism, and a summary of the number of subjects with polymorphisms in NS3 only, NS5A only, NS5B only, any in NS3, any in NS5A, any in NS5B, any in NS3 or NS5A or NS5B, any in NS3 + NS5A, any in NS3 + NS5B, any in NS5A + NS5B, and any in NS3 + NS5A + NS5B.
- Total number and percentage of subjects in the ITT population with baseline polymorphisms *in the key subset of amino acid positions* at detection thresholds of 15% for subjects in the ITT population. This analysis summarizes the number of subjects with polymorphisms in NS3 only, NS5A only, NS5B only, any in NS3, any in NS5A, any in NS5B, any in NS3 or

NS5A or NS5B, any in NS3 + NS5A, any in NS3 + NS5B, any in NS5A + NS5B, and any in NS3 + NS5A + NS5B.

Analysis 2

The impact of baseline polymorphisms at the *key subset of amino acid positions* on treatment outcome (the SVR₁₂ rate) will be assessed for the **mITT-VF** population by presenting the SVR₁₂ rates for the following groups, using detection thresholds of 2% and 15%, separated by arm, HCV genotype/subtype (including total), and previous treatment experience prior to enrolling in the AbbVie HCV parent study:

- in NS3 only versus none in NS3, NS5A, or NS5B
- in NS5A only versus none in NS3, NS5A, or NS5B
- in NS5B only compared to none in NS3, NS5A, or NS5B
- any in both NS3 and NS5A versus none in NS3 or NS5A
- any in both NS3 and NS5B versus none in NS3 or NS5B
- any in both NS5A and NS5B versus none in NS5A or NS5B
- any in each of NS3, NS5A and NS5B versus none in NS3, NS5A, or NS5B
- any in NS3 versus none in NS3
- any in NS5A versus none in NS5A
- any in NS5B versus none in NS5B
- any in NS3 or NS5A or NS5B versus none in NS3, NS5A, or NS5B

Analysis 3

The following listings will be produced for subjects who do not achieve SVR₁₂ or SVR₂₄ and have post-baseline resistance data available. HCV genotype/subtype and reason for SVR₁₂ or SVR₂₄ non-response will be displayed for each subject by treatment, and previous treatment experience prior to enrolling in the AbbVie HCV parent study.

- Listing by subject and time point of all *treatment-emergent substitutions* relative to the baseline amino acid sequence will be provided for each DAA target (NS3, NS5A, and NS5B).
- Listing by subject and time point of all *substitutions at signature amino acid positions* in a post-baseline time point relative to the appropriate prototypic reference amino acid sequence will be provided for each DAA target (NS3, NS5A, and NS5B).

HCV Genotype/Subtype

Phylogenetic analysis will be conducted on HCV sequences from baseline samples for all subjects in order to accurately determine subtype.

Subjects' HCV genotype and subtype may be assessed based on the Inno-LiPA 2.0 Assay used by the Central lab (Covance), the HCV genotype determination by Sanger sequencing a region of NS5B by the Central lab (Covance) and/or from phylogenetic analysis of the full length NS3/4A NS5A, and/or NS5B sequences performed by AbbVie. If the phylogenetic analysis is available, then it will be used to determine the subject's HCV genotype and subtype. If it is not available, then the Sanger sequencing assay result will be used to determine the subject's HCV genotype and subtype, if available. Finally, if neither the phylogenetic analysis result nor the Sanger sequencing assay results is available, then the Inno-LiPA assay results will be used to categorize the subject.

This subtype information will be presented in summaries of efficacy subgroup analyses.

A summary of HCV subtype as provided by the central laboratory (Sanger sequencing or Inno-LiPA 2.0 Assay [if Sanger sequencing not available]) versus phylogenetic analysis also will be provided if any differ.

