8.1.3 HCV Resistance Analyses

The genes of interest for NGS in this study are those encoding full length NS3/4A, NS5A and NS5B. For each DAA target, signature resistance-associated amino acid positions will be identified by AbbVie Clinical Virology. An appropriate prototypic reference sequence will be used for comparison with sequences from samples.

Only samples with an HCV RNA level of ≥ 1000 IU/mL will undergo sequence analysis in order to allow accurate assessment of products of amplification. Therefore, if the HCV RNA level at the time of HCV virologic failure or treatment discontinuation is < 1000 IU/mL, the sample closest in time after HCV virologic failure/treatment discontinuation with an HCV RNA level ≥ 1000 IU/mL will be used. Included time points for analyses on samples from subjects who do not achieve SVR₁₂ are 1) the sample closest in time after failure/discontinuation with an HCV RNA level of ≥ 1000 IU/mL,

and 2) 24 weeks post-DAA treatment, provided that resistance-associated variants were detected by NGS at the time of HCV virologic failure/treatment discontinuation.

The following definitions will be used in the HCV resistance analyses:

- Baseline variant: a variant (by NGS) in a baseline sample ($\geq 2\%$ or $\geq 15\%$ prevalence within a subject's viral population depending on variant frequency threshold utilized) that was not present in appropriate prototypic reference amino acid sequence for a given DAA target.
- Post-baseline variant: an amino acid variant in a post-baseline time point sample that was not detected at baseline ($< 2\%$) in the subject and is detectable in $\geq 2\%$ of the sequences from the post-baseline sample in a given DAA target.
- Enriched variant: variant present in both the baseline and a post-baseline sample whose prevalence in the post-baseline sample is at least 20 percentage points greater than the prevalence in the baseline sample [(post-baseline % – baseline %) ≥ 20]
- Treatment-emergent variant: A post-baseline variant or an enriched variant.
- Variant at signature amino acid position: variant (relative to reference) present in a baseline or a post-baseline sample at a signature amino acid position.

The following analyses will be performed for all subjects:

To characterize prior HCV DAA resistance patterns in the study population, available resistance analysis data obtained at the time of the subject's virologic failure of the previous DAA treatment will be collected and reported.

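### SAP 10.8.1 leaves NS5B out of baseline sequencing, so its baseline-NS5B and treatment-emergent NS5B analyses (the sofosbuvir target) cannot be done as written

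*SAP*

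**What the plan says.** The baseline rule in SAP 10.8.1 reads "For all subjects, full length NS3/4A and NS5A will be sequenced from baseline samples by next generation sequencing (NGS"). The next sentence, on virologic failures, covers "full length NS3/4A, NS5A and NS5B genes from the first sample after virologic failure with HCV RNA" at or above 1000 IU/mL. The sentence after that names the same three genes for other non-responders with a post-treatment sample at that level.

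The planned outputs in the same section then draw on three genes at baseline:

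- **Definition.** "Baseline polymorphism: a polymorphism by NGS in a baseline sample", with NS3, NS5A and NS5B given as the targets.
- **Analysis 1.** A listing of baseline polymorphisms "at signature amino acid positions for each DAA target (NS3, NS5A, and NS5B) in the ITT population", followed by counts in 11 gene categories.
- **Analysis 2.** SVR12 rates for 11 contrasts in the mITT-VF population, for example "in NS5B only compared to none in NS3, NS5A, or NS5B".
- **Analysis 3.** A listing of treatment-emergent substitutions in each of the three genes, judged against the subject's baseline sequence. A post-baseline substitution is defined as "an amino acid substitution in a post-baseline time point sample that was not detected at baseline" (below 2%).

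Protocol 8.1.3 states "The genes of interest for NGS in this study are those encoding full length NS3/4A, NS5A and NS5B" and makes no exception for baseline.

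**The concern.** The baseline sentence omits a gene that the following two sentences include and that the analyses require. Read literally, the plan produces no baseline NS5B sequence by NGS.

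Sofosbuvir, an NS5B inhibitor, is one of the two drugs added to ABT-493/ABT-530 in this retreatment regimen. Protocol 3.2 justifies the regimen partly by its additional mechanisms of action against resistant variants. The SAP also has prior-treatment categories for NS5B-inhibitor-experienced subjects, so NS5B variants already present at entry are a foreseeable question. If a subject fails with a change at position 282, the only key NS5B position in SAP Table 10, the study would need to say whether it arose on treatment or was there before. Without the baseline sequence it cannot.

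There is also a programming risk. If unsequenced NS5B were coded as no polymorphism, the groups with changes in one gene only and the polymorphism-free reference groups would be misclassified without any visible gap in the tables.

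**Working it through.** The plan gives no figure to reproduce. The check traces each output in SAP 10.8.1 to the baseline sequences it needs and counts those that need NS5B.

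**Analysis 2**

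| # | Carrier group | Reference group free of polymorphisms in | Needs baseline NS5B |
|---|---|---|---|
| 1 | NS3 only | all three genes | yes |
| 2 | NS5A only | all three genes | yes |
| 3 | NS5B only | all three genes | yes |
| 4 | NS3 and NS5A | NS3, NS5A | no |
| 5 | NS3 and NS5B | NS3, NS5B | yes |
| 6 | NS5A and NS5B | NS5A, NS5B | yes |
| 7 | NS3, NS5A and NS5B | all three genes | yes |
| 8 | any NS3 | NS3 | no |
| 9 | any NS5A | NS5A | no |
| 10 | any NS5B | NS5B | yes |
| 11 | any of the three | all three genes | yes |

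Rows needing NS5B: 11 − 3 = 8. In all 8 the reference group is conditioned on NS5B. Five (rows 1, 2, 3, 7, 11) use the reference free of polymorphisms in all three genes, and three (rows 5, 6, 10) use a narrower reference that still includes NS5B: 5 + 3 = 8.

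**Analysis 1.** The summary has 11 categories, used for both the signature positions and the key subset. Only any NS3, any NS5A, and NS3 with NS5A can be completed without NS5B, so 11 − 3 = 8 cannot. These 8 include the NS3-only and NS5A-only categories, because a polymorphism in NS5B has to be ruled out. The NS5B part of the baseline listing is also lost.

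**Analysis 3.** There are two routes to a treatment-emergent substitution: below 2% at baseline and at least 2% afterwards, or a rise of at least 20 percentage points over baseline. Both need the subject's own baseline sequence of that gene, so the NS5B treatment-emergent listing cannot be produced. The second listing compares post-baseline sequences with a prototypic reference and remains feasible for NS5B.

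**Could another source supply baseline NS5B?** Protocol 5.3.1.1 has a Sanger assay at screening, but it covers a region of NS5B, is run only when the LiPA assay cannot assign genotype or subtype, and is not NGS. It does not meet the SAP's NGS-based definition or its 2% and 15% thresholds. The genotype paragraph in SAP 10.8.1 mentions NS5B sequences with and/or wording, which commits to nothing.

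**Was the omission declared?** SAP 12.1 item 4 says in general terms that the resistance analyses were brought into line with project standards. It does not say that baseline NS5B sequencing was dropped.

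**The case against.** The strongest reply is that this is a dropped word. The SAP sentence does not say that only two genes will be sequenced, and the SAP describes itself as elaborating the protocol, which names NS5B and asks for baseline variants for each DAA target. The SAP's own definitions and Table 10 assume NS5B. On that reading the data may well exist. This stands as a point about intent: the documents do not prove that baseline NS5B will be missing. It does not remove the conflict, since anyone commissioning sequencing from the SAP would order two genes.

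A second reply concerns weight. Resistance is neither a primary nor a secondary endpoint, there is no hypothesis test, and SAP 4.3 expects fewer than 5 SVR12 non-responders, so the Analysis 3 listing may cover a handful of subjects. The baseline-variant subgroup in protocol 8.1.2.4 is no longer in SAP 10.6. A change at position 282 would still appear in the listing against the reference sequence. All of this is correct and limits the damage to the resistance outputs. With so few failures, however, the classification of each one carries most of the information.

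A third reply is that the omission may have been deliberate. The SAP incorporates country-specific amendments and an administrative change that were not available for this review. If so, the dependent outputs should have been changed as well, and they were not.

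**Conclusion.** The concern holds. Within SAP 10.8.1 the baseline sequencing rule and Analyses 1 to 3 contradict each other, and the rule also departs from protocol 8.1.3. As written, 8 of 11 Analysis 2 contrasts, 8 of 11 Analysis 1 summary categories, the NS5B part of the baseline listing and the treatment-emergent NS5B listing cannot be produced. SVR12, on-treatment virologic failure, relapse and safety are unaffected.

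The conclusion rests on reading the baseline sentence as the complete list of genes. The contrast with the two sentences that follow it, where NS5B is named each time, supports that reading. It makes no claim about what the laboratory will actually do. The text needs correcting before the resistance analyses are programmed.

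**What to change.** In SAP 10.8.1, add NS5B to the baseline sentence so that full-length NS3/4A, NS5A and NS5B are all sequenced from baseline samples by NGS, as protocol 8.1.3 provides. State as well that a subject without a usable baseline NS5B sequence is treated as missing for NS5B and not as free of polymorphisms.

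The cost is a small text change plus NS5B sequencing of about 50 baseline samples. Protocol 5.3.1.1 and Appendix C already schedule a pre-dose Day 1 resistance sample for every subject, so no protocol amendment or new visit is needed. This assumes that the samples are still available and meet the 1000 IU/mL minimum for sequencing in protocol 8.1.3.

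If baseline NS5B was dropped on purpose, remove or redefine the outputs counted above, including the reference groups that depend on NS5B, and record the departure from the protocol explicitly in SAP 12.1.
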